There is a gap between the best available scientific evidence provided by guidelines on syncope (1) and falls (2) and the need for the dissemination of these concepts into clinical practice. The multidisciplinary nature of faint and falls is the major barrier to the dissemination of guidelines and to a comprehensive management that covers all the aspects of faints and falls. The absence of a systematic global approach to faints and falls incurs higher health and social care costs, unnecessary hospitalizations and diagnostic procedures, prolongation of hospital stays, lower diagnostic rates, and higher rates of misdiagnoses and symptom recurrence.

2. Aims of the study.

To assess the effectiveness (adherence) of a patient flow pathway and cost of a guideline-based global approach to the management of faints and falls in patients referred to dedicated multidisciplinary outpatient facilities. We will considerer the following endpoints:

Primary-endpoint:

- I. Point and interval prevalence estimation of patients with unexplained falls (████), among those who underwent fall diagnostic assessment at initial presentation (██████), and then moved to faint pathway for prosecution of diagnostic assessment (Figure 1), and its determinants.

Secondary endpoints:

- I. Point and interval estimate of the agree proportion between initial presentation and final diagnosis in patients initially assigned to faint and those with unexplained falls.
- II. Descriptive comparison between patients initially assigned to faint and those with unexplained falls in terms of diagnostic assessment and adherence rate to the recommendations of the guidelines (see appendix).
- III. Descriptive cost analysis of the faint and fall protocol (costs of investigations per patient).

Moreover, all previous analysis will be performed also for predefined age subgroups (≥ 75 , 74-65 and 64-40 years).

3. Study design

Prospective observational study

Inclusion criteria

- Consecutive patients aged ≥ 40 years referred to the Faint & Fall Clinics for assessment of an episode of faint or fall. The possible hospitals to recruit patients are Istituto Auxologico Italiano and Ospedale di Careggi, University of Florence. The patients will be recruited from the second half of 2020 and the recruitment will continue until to the achievement of the sample size (defined below).

[figure not shown]
Exclusion criteria:

- Patients with age < 40 years
- Patients with incidental fall
- Patients with an established diagnosis of syncope
- Patients in whom syncope and fall are secondary symptoms of severe underlying comorbidities (e.g: acute myocardial infarction, pulmonary embolism, acute haemorrhage)

A screening log of excluded patients (Faint & Fall Registry) will be collected.

Patients' flow

Each included patient will undergo to the faint and fall protocol, to assess the effectiveness of a patients' flow pathways (shown in the figure 1) developed in accordance with the most recent guidelines on syncope of the European Society of cardiology (1) and of guidelines on falls of the American and British Geriatrics Societies (2). The detailed flow pathway is described in the Appendix.

The grey box will be not considered for the analysis of this study

Figure 1. Schematic description of the patients' flow pathways in the Faint & Fall multidisciplinary outpatient clinics

Abbreviations: OI=orthostatic hypotension; PPS=psychogenic pseudosyncope

4 Sample size

A sample size of 340 produces a two-sided 95% confidence interval with a width equal to 10% when the prevalence of unexplained falls is 30% (sample size calculated with software PASS 14 Power Analysis and Sample Size Software (2015). NCSS, LLC. Kaysville, Utah, USA, [ncss.com/software/pass.](http://ncss.com/software/pass/)).

This sample size will allow to calculate an interval estimate of the agree proportion between initial presentation and final diagnosis in patients initially assigned to unexplained falls with a width varying from 0.12 to 0.19 assuming a prevalence of agree varying from 0.9 to 0.6. Analogously, a sample of 100 unexplained faint will guarantee the same coverage.

5 Statistical analysis

Continuous data will be summarized by means of mean value and standard deviation (SD) if the variable follows a Normal distribution or median and interquartile range in case of non Normal distribution. Categorical data will be summarized by means of absolute and relative frequencies.

For primary endpoint we will calculate the proportion of unexplained fall and its 95% interval confidence through normal approximation method. The same calculation will be carried out for the agree proportion between initial presentation and final diagnosis in patients initially assigned to faint and those with unexplained falls. Finally, to detect the determinants of unexplained falls at initial presentation we will apply a linear discriminant analysis [5].

6 References

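### The normal-approximation interval fixed in Section 5 under-covers when agreement is high, above all in the age subgroups, and it is not the method under which 340 is the required sample size; the Wilson interval mends both without more patients

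*Protocol*

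**What the plan says.** Protocol, Section 4 (Sample size), gives the primary sizing: "A sample size of 340 produces a two-sided 95% confidence interval with a width equal to 10" per cent "when the prevalence of unexplained falls is 30" per cent. It names the software (PASS 14) but no interval formula. The next paragraph turns to agreement between initial presentation and final diagnosis among unexplained falls and expects an interval "with a width varying from 0.12 to 0.19 assuming a prevalence of agree varying from 0.9 to 0.6". It adds that "a sample of 100 unexplained faint will guarantee the same coverage".

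Section 5 (Statistical analysis) names the method: "we will calculate the proportion of unexplained fall and its 95% interval confidence through normal approximation method". It extends this to the secondary endpoint: "The same calculation will be carried out for the agree proportion between initial presentation and final diagnosis".

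Section 2 (Aims of the study) has all these analyses repeated in three age groups: 75 and over, 65 to 74, and 40 to 64 years.

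**The concern.** Two things stand out when Sections 4 and 5 are read together.

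- **Sizing and analysis do not line up.** The protocol states both a number and a method, and the method does not return the number as the one required for the stated width.
- **The method is weak where the protocol expects to use it.** The simple normal approximation, estimate ± 1.96 standard errors, is adequate at 30% of 340. It deteriorates as the proportion nears 1 and the denominator shrinks. The protocol plans for agreement up to 0.9, in about 100 patients, and then splits them by age.

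This is an estimation study, and its intervals are its main inferential product. An interval labelled 95% that covers well below 95% overstates how precisely agreement is known in the older and younger groups.

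**Working it through.** **Inputs.** From Section 4: n = 340, prevalence 0.30, width 0.10, agreement 0.6 to 0.9, 100 faint patients. From Section 5: normal approximation; a continuity correction is neither stated nor excluded. Derived, not printed: 0.30 × 340 = 102 unexplained falls. Assumed: 102 / 3 = 34 per age group.

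**1. The plan's own figures under the planned method.** Width = 2 × 1.96 × √(p(1−p)/n).
- n = 340, p = 0.30: 3.92 × √(0.21/340) = 0.0974, which prints as 10% to the whole per cent.
- n = 102: 0.116 at p = 0.9 and 0.190 at p = 0.6. n = 100: 0.118 and 0.192. Both pairs print as 0.12 and 0.19.

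**2. The n required for a width of 0.10.** Normal approximation: 1.96² × 0.21 / 0.05² = 322.7, so 323. Other methods:

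| Method | Smallest n | Width at 340 | Widths at n = 102 (p = 0.9; 0.6) |
|---|---|---|---|
| Normal approximation | 323 | 0.0974 | 0.116; 0.190 |
| Normal, continuity-corrected | 343 | 0.1004 | 0.126; 0.200 |
| Wilson | 320 | 0.0970 | 0.118; 0.187 |
| Wilson, continuity-corrected | 340 | 0.0999 | 0.127; 0.196 |
| Exact (Clopper-Pearson) | 341 | 0.1000 | 0.126; 0.1975 |

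As a required number, 340 belongs with the exact and continuity-corrected formulas. The 0.12 to 0.19 range belongs with the uncorrected ones.

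**3. Coverage.** For true agreement p, coverage is the sum of the binomial probabilities of all counts x whose interval contains p.

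| n | p | Normal approximation | Wilson |
|---|---|---|---|
| 340 | 0.30 | 94.8% | 94.9% |
| 102 | 0.60 | 94.6% | 94.6% |
| 102 | 0.80 | 94.6% | 95.4% |
| 102 | 0.90 | 93.7% | 95.5% |
| 100 | 0.90 | 93.2% | 93.6% |
| 34 | 0.80 | 91.9% | 95.0% |
| 34 | 0.90 | 86.2% | 95.2% |

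The loss at n = 34, p = 0.90 can be followed by hand.
- With 33 of 34 in agreement the estimate is 0.971 and the standard error √(0.971 × 0.029/34) = 0.029. The interval is 0.914 to 1.027: it misses 0.90 and runs past 1.
- With 34 of 34 the interval has zero width at 1.
- These two outcomes have probability 34 × 0.1 × 0.9³³ + 0.9³⁴ = 0.105 + 0.028 = 0.133. Counts of 25 or fewer also miss and add about 0.005. Coverage is 1 − 0.138 = 0.862.
- The Wilson intervals for 33 and 34 of 34 are 0.851 to 0.995 and 0.898 to 1.000. Both contain 0.90.

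**4. Sensitivity to the assumed subgroup size.** Coverage moves irregularly with n. At p = 0.90 the normal approximation gives 80.8% (n = 30), 87.1% (n = 35) and 91.5% (n = 40). Wilson gives 97.4%, 92.0% and 94.3%. Averaged over p from 0.60 to 0.90 in steps of 0.01, the normal approximation gives 92.2% at n = 34 and 94.2% at n = 102. Wilson gives 95.1% and 95.0%.

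**The case against.** The strongest reply is that nothing printed is wrong. Section 4 says that 340 produces a 10% width, not that 340 is the smallest number that does. Under the planned method 340 gives 9.7%, slightly better than promised, and the agreement widths come out as printed. The primary interval covers 94.8%. In the full group of unexplained falls the shortfall at 0.90 is just over one point, and at 0.6 there is none to speak of. In the faint group of 100, Wilson gains only 0.4 points at 0.90. The study is descriptive, and no test depends on these intervals.

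Most of this stands, and it rules out three stronger readings that a reader might infer:
- **That 340 is a miscalculation.** It reproduces under standard exact and continuity-corrected formulas, and it exceeds what the planned method needs by 17 patients.
- **That the stated widths cannot hold under one method.** At the printed precision, both the normal approximation and Wilson give 10%, 0.12 and 0.19 together. It is true only that none of the five methods checked makes 340 the required number and also gives 0.12 to 0.19.
- **That the exact interval sized the study.** The formula is not named, and the continuity-corrected Wilson interval fits at least as well. A change of method between the two paragraphs is plausible but not stated.

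The reply does not answer the age subgroups. The protocol commits to repeating the agreement analysis there, with a method whose coverage is poor at an agreement level it treats as plausible.

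**Conclusion.** The point holds as a modest improvement that costs no patients. The sizing mismatch is 323 against 340, or 9.7% against 10%; it is conservative and loses no precision. The coverage shortfall matters more. At agreement of 0.90 it is about 1.3 points at n = 102 (93.7%) and about 9 points at n = 34 (86.2%). Wilson stays near nominal on average, though not at every n.

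The conclusion rests on two figures that the protocol does not print: 102 unexplained falls, and equal age thirds of 34. Unequal groups would change the subgroup coverage: between 30 and 40 patients the values checked run from 80.8% to 91.5%. If agreement is nearer 0.6, the two methods hardly differ. The primary estimate is sound under either.

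**What to change.** In Section 5, replace the normal approximation with the Wilson score interval for the primary proportion, the agreement proportion in both groups, and the same quantities by age group.

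In Section 4, name the Wilson interval as the method behind the stated precision, and restate the primary width at 340 patients as 9.7%. Printing the 102 unexplained falls on which the agreement widths appear to rest would let a reader check them.

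Nothing else moves. The sample size stays at 340. The Wilson agreement widths are 0.118 and 0.187 at n = 102, and 0.119 and 0.189 at n = 100, so 0.12 to 0.19 stands. The cost is a few words in two sections and an interval that is no longer symmetric about the estimate.

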f) Vitamin D supplement of at least 800 IU per day in patients with proven vitamin D deficiency in order to reduce the fracture rate (high evidence)

g) Management of postural hypotension (spontaneous or drug-induced) (high evidence). Require full cardiovascular autonomic assessment (refer to syncope pathway for diagnosis and treatment)

Dementia. There is insufficient evidence to recommend for or against multifactorial or single interventions to prevent falls in older persons with known dementia

B) Faint assessment

Patients with unexplained fall perform the same evaluation as for faint

B1. Initial evaluation

To all:

- **history**
- **physical examination** (including standing BP)
- **standard ECG**
- **echocardiogram** (if SHD is suspected)

The initial evaluation should be able to classify the patient in one of the following categories (primary end-point):

- Certain or highly likely diagnosis (if class I diagnostic criteria are met)
- Cardiac likely, to be confirmed by tests
- Cardiac unlikely, reflex or orthostatic hypotension likely to be confirmed by tests
- No diagnosis (unexplained syncope), to be investigated by tests
- Non-syncopal faint

B2. Early evaluation

In selected cases (when appropriate):

- **basic CV autonomic function tests** (if OH or NMS are suspected):
 - 3 min active standing test
 - Valsalva manoeuvre and deep breathing
 - carotid sinus massage (in pts >40 years)
 - tilt testing
 - ambulatory BP monitoring
 - **prolonged ECG home monitoring** (if arrhythmia is suspected)
 - **blood tests** (pO₂ & gas analysys, haematocrit & blood cells count, troponin, d-dimer)
 - **exercise test** (if syncope had occurred during physical effort)

B3. Subsequent evaluation

When indicated, in accordance with the recommendations of ESC guidelines on syncope (secondary end-point):

- **Home video recording**
- **Implantable loop recorder**
- **Electrophysiological study**
- **Coronary angiography**

B4. Faint prevention therapy and follow-up

When indicated, in accordance with the recommendations of ESC guidelines on syncope (secondary end-point) (Figure 3):

Treatment of syncope: General principles

[figure not shown]

Figure 3

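### Section 5's Normal/non-Normal rule would probably report secondary endpoint III (investigation cost per patient) as median and IQR, without the average cost that the aim calls for

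*Protocol*

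**What the plan says.** The aim (Protocol, section 2) covers both the effectiveness of the "patient flow pathway and cost of a guideline-based global approach to the management of faints and falls". Secondary endpoint III turns the cost part into a "Descriptive cost analysis of the faint and fall protocol (costs of investigations per patient"), and section 2 repeats every analysis in three age groups.

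Section 5 (Statistical analysis) never mentions cost. Its rule for continuous data is mean and SD where the variable is Normal, and "median and interquartile range in case of non Normal distribution". It makes no exception for cost and names no other cost statistic, such as a total, a mean or an interval.

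Appendix B describes how investigations accumulate in the faint pathway. Initial evaluation (B1) is for everyone. Early evaluation (B2) is done "In selected cases (when appropriate"). Subsequent evaluation (B3), which includes "Implantable loop recorder", electrophysiological study and coronary angiography, is done only when indicated. Unexplained falls follow the same route: "Patients with unexplained fall perform the same evaluation as for faint".

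**The concern.** Cost per patient is a continuous variable, so the section 5 rule applies to it unless an exception is stated. A work-up in which everyone has the basic tests and some patients have additional, dearer ones tends to produce a long right tail. The rule then selects median and IQR.

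For most variables that is sensible description. For cost it loses the quantity of interest. Total cost equals the number of patients times the arithmetic mean, and neither can be recovered from the median and quartiles. If a costly test is used in a small share of patients, the reported summary can be almost the same whatever that test costs. A reader wanting to know what the guideline-based approach costs per patient would not find the figure that scales to a clinic.

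**Working it through.** The protocol gives no cost figure to reproduce. Whether the rule applies follows from the text; the size can only be illustrated.

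**Step 1. Does the rule reach cost?** Endpoint III is a per-patient amount, hence continuous. Section 5 has one rule for continuous data and no exception. Read as written, it does.

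**Step 2. Is non-Normality likely?** B1 goes to all, B2 to selected cases, B3 only when indicated. The expected shape is a common base cost with dearer tests added in some patients. This is an inference from structure, not from data.

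**Step 3. Illustration, faint pathway only (faint and unexplained falls). All cost inputs are assumed.**
- Base work-up: lognormal, median 300 units, SD of the log 0.4. Base mean = 300 × exp(0.4²/2) = 325.
- One costly test at price *c*, used in a share *f* of patients.
- Mean = 325 + *f* × *c*.
- While patients with the test all lie above the quantile in question, the *p*-quantile is 300 × exp(0.4 × *z*), where *z* is the standard Normal quantile at *p*/(1 − *f*). The price *c* does not appear in it.

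*Test in 20% (f = 0.20):*
- Lower quartile: 0.25/0.80 = 0.3125, *z* = −0.489, giving 247.
- Median: 0.50/0.80 = 0.625, *z* = 0.319, giving 341.
- Upper quartile: 0.75/0.80 = 0.9375, *z* = 1.534, giving 554.
- Mean at *c* = 500: 325 + 100 = 425. Mean at *c* = 5,000: 325 + 1,000 = 1,325.

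A tenfold price rise roughly triples the mean and leaves all three quartiles where they were.

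*Price of 2,500 units, varying use:*

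| Use of test | Mean | Median | Upper quartile | Median as % of mean |
|---|---|---|---|---|
| 5% | 450 | 308 | 414 | 68% |
| 15% | 700 | 328 | 482 | 47% |
| 20% | 825 | 341 | 554 | 41% |
| 30% | 1,075 | 376 | 2,704 | 35% |

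At 30% use more than a quarter of patients have the test, so the upper quartile falls among them: (0.75 − 0.70)/0.30 = 0.167, *z* = −0.967, giving 2,500 + 204 = 2,704. The IQR then shows the costly test, although the median is still about a third of the mean.

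*Price of 500 units:* at 5%, 15%, 20% and 30% use the median is 88%, 82%, 80% and 79% of the mean.

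**Step 4. What depends on the assumptions?** The ratios do. The structural result does not: if a clearly separated costly test is used in fewer than about a quarter of the patients summarised, its price barely enters any reported quartile.

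**The case against.** The strongest case against is that section 5 gives a general descriptive convention, not a deliberate choice for cost. It does not forbid a mean as well, and details of a cost analysis are often left to a statistical analysis plan. The protocol never promises an average, a total or a comparison of costs, so the mean as target is inferred from the aim. Endpoint III could also mean total cost divided by number of patients, which is already a mean. Test frequencies reported under secondary endpoint II would partly offset the loss.

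Much of this stands, and it keeps the point minor. It does not remove it. The rule is stated, covers cost as worded, and would carry over into any analysis plan that follows it. If endpoint III already means total over patients, the fix merely confirms that.

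Three stronger readings are tempting and not supported:
- **A share for the whole protocol.** A reader might take section 4's 30% of 340 (102 unexplained falls) plus 100 faint patients as the planned faint-pathway group, 202 of 440 or 46%, and work out mean-to-median gaps over all patients. Section 4 says only that "a sample of 100 unexplained faint will guarantee the same coverage". That is a conditional statement about precision, possibly about a subset of faint patients, and does not fix how many enrol. Figure 1 is not shown, and its grey box is outside the analysis, so the patients to be costed are not known here.
- **Median and IQR always hide the costly tests.** They do not: at 30% use the upper quartile shows the test clearly.
- **The protocol contradicts itself.** It does not. A general rule fits one endpoint poorly.

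**Conclusion.** The point holds as a minor, nearly free improvement. Applied as written, section 5 would probably summarise endpoint III by median and IQR and leave out the average cost that the aim calls for. The size cannot be established from the protocol. Under the assumed faint-pathway costs, the median runs from 88% of the mean (500-unit test, 5% use) down to 35% (2,500-unit test, 30% use). These figures rest on assumed prices and usage, one costly test, and a lognormal base; several selective tests combined could give a different shape. Data collection, the primary endpoint and the sample size are unaffected, and a mean can still be computed from the same data. The gain lies in fixing the statistic before the data are seen.

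**What to change.** Add one sentence to section 5: for secondary endpoint III, the arithmetic mean cost per patient, with SD or a bootstrap 95% confidence interval, is reported whatever the distribution, overall and in the age groups already planned, with median and IQR as supplementary description. The cost is one sentence and a little extra analysis on data already to be collected.

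### The normal-approximation interval fixed for the agreement proportions falls short of 95% coverage in the age subgroups if agreement is near 0.9 (86% at n = 34, assuming an equal split)

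*Protocol*

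**What the plan says.** Protocol Section 5 prescribes, for the primary proportion, "its 95% interval confidence through normal approximation method. The same calculation will be carried out for the agree proportion". Agreement here means that the classification at presentation matches the final diagnosis, estimated separately for the faint group and the unexplained-fall group. That agreement estimate, with its interval, is secondary endpoint I in Section 2.

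Section 2 then adds that "all previous analysis will be performed also for predefined age subgroups": 75 and over, 65 to 74, and 40 to 64 years.

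Section 4 sets the planning values. The total of 340 applies "when the prevalence of unexplained falls is 30"%. The agreement interval among unexplained falls is planned "with a width varying from 0.12 to 0.19 assuming a prevalence of agree varying from 0.9 to 0.6". For the other group, "a sample of 100 unexplained faint will guarantee the same coverage".

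The protocol names no other interval method for small groups or for proportions near 1, and it gives no band sizes.

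**The concern.** The Wald interval is centred on the observed proportion and takes its width from that same proportion. When the true proportion is high and the sample is small, both features work against it. A sample with few disagreements is centred too high and also gets too narrow an interval, down to zero width when everyone agrees. The whole groups, at about 100 patients, are large enough for this to matter little. One third of such a group may not be.

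At stake is the error bar on secondary endpoint I within each age band. This endpoint describes how well the initial classification matches the final diagnosis. An interval that is labelled 95%, but misses well over 5% of the time and almost always on the high side, would make the pathway look more reliable in that band than the data support. Limits above 100% or of zero width would also be visible defects in a published table.

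**Working it through.** **Inputs**
- Unexplained falls: 340 × 0.30 = 102 (Section 4).
- Faints: 100 (Section 4).
- Agreement p between 0.6 and 0.9 (Section 4).
- Three age bands (Section 2).
- Two-sided 95%, z = 1.96.
- Assumption: equal split, so 102/3 = 34 and 100/3 ≈ 33 per band. At these totals the smallest band cannot exceed those sizes. Other sizes are scanned below.

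**The plan's own figures**

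Wald width = 2 × 1.96 × √(p(1−p)/n). At n = 102:
- p = 0.9: 3.92 × √(0.09/102) = 0.116.
- p = 0.6: 3.92 × √(0.24/102) = 0.190.

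These match the stated 0.12 to 0.19, so 102 is the group size the protocol had in mind.

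**Exact coverage at n = 34, p = 0.9**

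Coverage is the sum of binomial(34, 0.9) probabilities over every count x whose interval contains 0.9.
- Wholly above 0.9: x = 33 (0.914 to 1.027), probability 34 × 0.9³³ × 0.1 = 0.105; and x = 34 (1.000 to 1.000), probability 0.9³⁴ = 0.028. Total 0.133.
- Wholly below 0.9: x ≤ 25 (at x = 25 the upper limit is 0.884; at x = 26 it is 0.907). Total 0.005.
- Coverage: 1 − 0.133 − 0.005 = 0.862.
- Upper limit above 1: x = 31, 32 or 33 (limits 1.007, 1.020, 1.027). Total probability 0.526.

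**Comparison with the Wilson score interval**

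| n | p | Wald | Wilson |
|---|---|---|---|
| 34 | 0.90 | 86.2% | 95.2% |
| 34 | 0.85 | 89.4% | 94.8% |
| 34 | 0.80 | 91.9% | 95.0% |
| 33 | 0.90 | 85.2% | 95.8% |
| 102 | 0.90 | 93.7% | 95.5% |
| 100 | 0.90 | 93.2% | 93.6% |

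At n = 34 and p = 0.6, 0.7 or 0.75, Wald coverage is about 94% to 95%. For the primary endpoint (n = 340, p = 0.3) it is 94.8%.

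**Uneven splits: every n from 20 to 50**

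| p | Wald mean | Wilson mean |
|---|---|---|
| 0.90 | 89.8% (range 81% to 95%) | 95.7% (range 92% to 98%) |
| 0.85 | 90.6% | 95.4% |
| 0.80 | 92.3% | 95.3% |
| 0.60 | 93.7% | 95.1% |

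At p = 0.9, Wald is below 90% at 15 of the 31 sizes.

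**What a table would show**
- 34 of 34 agreeing: Wald 100% to 100%, Wilson 89.8% to 100%.
- 31 of 34 agreeing: Wald 81.6% to 100.7%, Wilson 77.0% to 97.0%.

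**The case against.** **The 86% is one point on a jagged curve.** At p = 0.9, coverage is 94.7% at n = 29, 80.9% at n = 30 and 95.0% at n = 47. This is true, and the average of about 90% over n = 20 to 50 is the better summary. That average is still twice the nominal error rate.

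**It needs agreement near the favourable end of the range.** Averaged evenly over p = 0.6 to 0.9 at n = 34, Wald coverage is 92.4%, a mild shortfall, and the protocol marks no value as expected. This also stands. But 0.9 is the sponsor's own planning value, and a method fixed in advance should work across the range it was planned for.

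**Group sizes are not guaranteed.** The figure of 100 faints says what that number would deliver and is not a cap. The 102 holds only if prevalence is 30%. The band sizes are therefore conditional on the planning figures. Larger groups would ease the problem, but not steadily: at p = 0.9 coverage is 87.9% at n = 50 and 91.2% at n = 68.

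**Section 5 does not mention the age bands, and a SAP could add rules for small groups.** Section 2 says that all the analyses are repeated by band, so the natural reading carries the Section 5 method into the bands. The method is stated in the protocol and is not a detail left open.

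**Little hangs on it.** The endpoint is secondary and descriptive, with no test or decision rule attached. That is a fair reason to rank the point low, but not to leave the interval as it is.

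**Conclusion.** The concern holds, as a minor point. Following the protocol as written produces Wald intervals for agreement in bands of roughly 34 patients. If true agreement is near 0.9, these cover about 90% of the time on average over n = 20 to 50, and 86.2% at n = 34. Of the 13.8% that miss at n = 34, 13.3 percentage points lie wholly above the true value.

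The size of the problem rests on three things: the planning totals of 102 and 100, a roughly even split across bands (assumed), and agreement of about 0.8 or higher. The primary prevalence is unaffected, and whole-group agreement loses only one to two percentage points of coverage.

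**What to change.** In Section 5, state that the 95% interval for the agreement proportion, overall and in each age subgroup, will be calculated by the Wilson score method in place of the normal approximation. The gain is in the subgroups. Using the same method overall keeps the tables consistent, although at n = 100 and p = 0.9 it changes coverage very little. The primary prevalence can keep the normal approximation.

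The cost is one sentence, with no extra patients or data. The precision claims in Section 4 survive: Wilson widths are 0.118 to 0.187 at n = 102 and 0.119 to 0.189 at n = 100, which still round to 0.12 to 0.19. An exact (Clopper-Pearson) interval would also cure the undercoverage, but it is conservative at this size (98.3% at n = 34, p = 0.9).
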